### 5.3 Treatment period

After all screening assessments have been completed and the patient's eligibility has been confirmed and documented, the patient will be enrolled.

**The following assessments should be performed on the first day of each cycle (FOLFIRINOX + Regorafenib except C1D1 prior to receiving study treatment (+/- 3 days) :**

- DLTs assessment for phase I from C2D1 to C4D1 (three first cycles),
- Physical examination with weight, body surface area (if the patient's body weight changes by more than 10 % then BSA will be recalculated for Regorafenib and it will be recalculated for any change of weight for Irinotecan). The physical examination includes skin assessment for toxicities,
- ECOG performance status,
- Adverse events documentation (including Start/Stop dates, seriousness, CTC notation and grading, relationship to study drug, outcome and action taken) using CTCAE V5.0,
- Concomitant medications (including start/stop dates, dose, indication),

- 12-lead ECG : It will be performed before and after oxaliplatin administration during the three first cycles of Phase I/II,
- The following laboratory evaluations are not required at Day 1 of Cycle 1 if these were completed within 7 days of starting study drug treatment. Otherwise, these laboratory evaluations are required on Day 1 of each cycle:
  - ➔ CBC with differential should be performed: RBC, hemoglobin, hematocrit, platelet count and WBC. WBC must include differential neutrophil, lymphocyte, monocyte, basophil and eosinophil counts,
  - ➔ Coagulation panel: Prothrombin time (PT) or the International Ratio of PT (PT-INR) and Partial Thromboplastin Time (PTT)  
If a patient is on warfarin or phenprocoumarone with stable PT/INR at baseline, the PT/INR should be assessed on Day 15 of Cycle 2. If either of these values is above the acceptable range, the doses should be modified and the assessments should be repeated every fortnight until it is stable,
  - ➔ Electrolyte panel: sodium, potassium, chloride, magnesium, calcium, bicarbonates, phosphate,
  - ➔ Chemistry panel : albumin, lipase, glucose, serum creatinine, clearance calculated according MDRD, uric acid, , protein total, TSH every 6 weeks,
  - ➔ Hepatic panel: Aspartate Amino-Transferase (AST), Alanine Amino-Transferase (ALT), bilirubin (total and direct), GGT, alkaline phosphatase, Lactic Dehydrogenase (LDH).
- Urine analysis: PH, protein, glucose, bilirubin, ketones, blood cells and leukocytes
- Drug dispensing,

- Drug accountability (pharmacy). To have complete control over the distribution and use of the study drug, the drug accountability must be performed on Day 1 for (Regorafenib) of each cycle.

A patient's diary is given on C1D1. It will allow to patient to write down his oral intakes and blood pressure values. It will be checked out at each cycle by C2D1.

- The blood pressure must be monitored every other week for the three first cycles of study treatment,

The blood pressure will be recorded by the patient and entered onto his treatment diary. Blood pressure measurements will be performed in patients sitting for 5 minutes prior to the evaluation.

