### 5. Visit Schedule

#### 5.1 Tabulated overview

Tabulated overview Folfirinox-R - Phase I/II	Screening		Treatment						Evaluation (Every 8 weeks)	End of treatment	Safety Follow-up	Follow-up	End of study
	D-21	D-7	Cycle 1		Cycle 2		Cycle 3		≥Cycle 4				
Cycles		C1D1	C1D8	C2D1	C2D8	C3D1	C3D8	≥C4					
Baseline documentation													
Informed consents 	X												
Demographics	X												
Complete medical history	X												
Eligibility Criteria checked 	X	X											
Physical examination 	X	X	X		X		X		X	X	X	X	
β-HCG blood test 			X										
Laboratory Studies													
12-lead ECG 	X		X 		X		X		X		X		
Complete blood count		X	X 	X	X	X	X	X			X		
Coagulation		X	X 		X		X		X		X		
Electrolyte panel		X	X 		X		X		X		X		
Chemistry panel 		X	X 	X	X	X	X	X			X		
Liver function test 		X	X 	X	X	X	X	X			X		
Tumor markers (ACE and CA 19-9)		X								X	X	X	

Tabulated overview Folfirinox-R - Phase I/II	Screening		Treatment						Evaluation (Every 8 weeks)	End of treatment	Safety Follow-up	Follow-up	End of study	
	D-21	D-7	Cycle 1		Cycle 2		Cycle 3		≥Cycle 4					
	Cycles		C1D1	C1D8	C2D1	C2D8	C3D1	C3D8	≥C4					
Urinary analysis 		X	X		X		X		X		X			
cfDNA analysis for RAS, UGT1A1 and serum uracil for evaluating DPD	X													
Imaging assessments														
Radiologic Tumor assessment 	X									X 	X 	X 		
Other Clinical Assessments														
DLT assessment 					X		X		X					
ECOG		X	X		X		X		X		X			
Body weight, BSA, height 		X	X		X		X		X	X	X			
Blood pressure 		X	X		X		X				X	X		
Concomitant medications		X	X		X		X		X		X	X		
Adverse events 		X	X		X		X		X		X	X	X 	
Drug dispensing			X		X		X							
Drug accountability					X		X		X		X			
Post-study survival status											X	X		
Anti-cancer medications											X	X		
Patient's diary checking 					X		X		X		X			
Ancillary studies														
EDTA tubes (3 X 7 ml) cfDNA 		X								X	X			
Paraffin block for analysis of DDR1 														X

Written informed consent will be obtained for pre-screening and for full study

Eligibility criteria will be checked for pre-screening and for full study

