### **FOLFIRINOX administration (Phase I and II):**

**FOLFIRINOX** will be administered as per standard procedures: every 14 days (**1 cycle = 14 days**):

- Oxaliplatin (Eloxatin® or generic drug): 85mg/m^2 on day 1, IV infusion over 2 hours, immediately followed by
- Folinic acid 400 mg/m^2 or Calcium Levofolinate 200mg/m^2 given as a 2-hour IV infusion, with the addition, after 30 minutes of
- Irinotecan (Campto® or generic drug): 150-180 mg/m^2 as per dose-level, given as a 90-minute intravenous infusion through a Y-connector immediately followed by
- 5-Fluorouracil: 400mg/m^2 IV bolus then 2400mg/m^2 over 46 hours continuous infusion.

Irinotecan infusion has to be preceded by a subcutaneous injection of atropine: 0.25mg to prevent cholinergic syndrome (in absence of contraindication).

[figure not shown]
The next cycle starts on day 15. Each cycle will be delivered every 2 weeks.

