## 6.4 Treatment duration

12 cycles have to be delivered consecutively or not.

Indeed, treatment can be temporarily stopped to perform surgical resection or regional procedures (radiofrequency, cryoablation, radiation therapy) if the disease become accessible to them but if it happens, before the end of the 12 planned cycles, the treatment

has to be resumed within 4 to 8 weeks after the loco-regional procedure has been completed in order to reach a total number of 12 cycles delivered.

If a surgery or a regional procedure is considered, we recommend respecting a time period of 4 weeks between the last chemotherapy and the procedure.

After 12 cycles, patients whose metastases are not progressing and are still unresectable will receive regorafenib (experimental regimen and at the same dose) until progression or toxicity.

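### Schedule table 5.1 leaves the blood count, chemistry and liver rows blank from cycle 4, while section 5.3 requires these tests at every cycle

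*Combined protocol and SAP*

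**What the plan says.** Section 5.3 lists the assessments due on the first day of each cycle. The laboratory list contains the blood count with differential, coagulation, electrolytes, chemistry and the hepatic panel. It is waived at day 1 of cycle 1 if done within the previous 7 days. Beyond that, "Otherwise, these laboratory evaluations are required on Day 1 of each cycle". The lead sentence sets the timing as "prior to receiving study treatment (+/- 3 days" (the parenthesis closes after a space in the original) and describes the cycle as FOLFIRINOX plus regorafenib.

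In table 5.1 the rows "Complete blood count", "Chemistry panel" and "Liver function test" are marked at D-7, at days 1 and 8 of cycles 1 to 3, and at end of treatment. None has a mark in the ≥C4 column.

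Section 6.6 uses the results. Table 4 makes the start of the next cycle, and its doses, depend on a blood count at D15. Table 9 adjusts regorafenib on neutrophils and platelets, and Table 10 on transaminases and bilirubin. None is restricted to the first three cycles. Section 6.1 states "The next cycle starts on day 15", so the D15 count is the pre-dose count of the following cycle. Section 6.4 states "12 cycles have to be delivered consecutively or not", after which patients who are not progressing and remain unresectable continue on regorafenib.

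**The concern.** Sites often work from the schedule table. Read alone, this one asks for coagulation and electrolytes from cycle 4 but not for neutrophils, platelets, creatinine, lipase, transaminases or bilirubin. A site reading section 5.3 would do all of them.

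Two things are at stake. The first is patient safety, because the omitted results are those that Tables 4, 9 and 10 act on. The second is the safety data. Safety of the combination is a phase II secondary objective (section 2.1.2), and haematological and hepatic abnormalities without symptoms are found only by testing. If sites follow different parts of the protocol, laboratory toxicity after cycle 3 is ascertained unevenly, and a low late rate could reflect fewer tests rather than fewer events.

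**Working it through.** The protocol states no figure for this point, so there is nothing to reproduce. The check compares the rows of table 5.1 with the text and then counts cycles.

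**Step 1: rows of table 5.1**, read against its 14 visit columns (D-21, D-7, days 1 and 8 of cycles 1 to 3, ≥C4, evaluation, end of treatment, safety follow-up, follow-up, end of study).

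| Row | Marked at | ≥C4 |
|---|---|---|
| Blood count | D-7; D1 and D8 of C1–C3; end of treatment | blank |
| Chemistry | same | blank |
| Liver function | same | blank |
| Coagulation, electrolytes | D-7; D1 of C1–C3; ≥C4; end of treatment | marked |
| ECG | D-21; D1 of C1–C3; ≥C4; end of treatment | marked |
| Urine | D-7; D1 of C1–C3; ≥C4; end of treatment | marked |

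**Step 2: is this a column shift?** The three rows read as 13 cells against 14 columns, so alignment has to be shown.

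- Their D8 marks match the day-8 list in section 5.3 (cycles 1, 2 and 3), and their last mark matches section 5.4.
- The tumor-marker row, in the same part of the table and also 13 cells long, falls at D-7, evaluation, end of treatment and safety follow-up. That agrees with sections 5.2 to 5.5 and places the missing cell at the end of the row.
- The coagulation and electrolyte rows, also 13 cells long, do carry a ≥C4 mark.
- In the second part of the table, the DLT row falls at C2D1, C3D1 and ≥C4, as section 5.3 describes (C2D1 to C4D1).

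The blanks therefore look genuine, subject to a look at the PDF.

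**Step 3: extent.**

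- Planned chemotherapy cycles: 12 (section 6.4). Cycles 4 to 12: 12 − 3 = 9. Share: 9/12 = 75%.
- Retreatment decisions (cycles 2 to 12): 12 − 1 = 11. Those under the blank column: 9. Share: 9/11 = 82%.
- Regorafenib maintenance cycles come on top, in a number that varies by patient.

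**Step 4: what the rest of the protocol requires.** Section 5.3 and Table 4 each call for a blood count before every chemotherapy cycle, so the number of FOLFIRINOX retreatment decisions with no required count anywhere in the protocol is 0 of 11. Section 5.3 also requires chemistry and liver tests at each cycle. The defect is a contradiction between table and text; the requirement itself is present.

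**The case against.** The best reply is that the blanks are clerical and no site would act on them. The drug dispensing row is also blank at ≥C4, although regorafenib plainly continues, so a blank in this table cannot be taken to mean stop. Footnote 6, attached to the chemistry row, sets TSH every 6 weeks on day 1. Three 14-day cycles are 42 days, so six weeks after C1D1 is C4D1, and the footnote itself implies sampling in the blank column. Adverse events are collected continuously and their row is marked at ≥C4. All of this makes an oversight likely. It does not remove the contradiction, and continuous event collection does not detect a laboratory abnormality that nobody measured.

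A reader might go further than the documents allow in three ways.

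- One might infer that most retreatment decisions have no reliable result behind them. Step 4 shows otherwise: section 5.3 and Table 4 still call for the count.
- One might read the ± 3 days in section 5.3 as permission to test up to three days after dosing. The same phrase requires the assessments before treatment, and Table 4 could not delay a cycle on a count taken after it. A tolerance on the visit date is the natural reading. The wording is loose, since a plus side sits awkwardly beside a pre-dose requirement, but it is at most an ambiguity.
- One might extend the count to week 48: 48/2 = 24 cycles, of which 24 − 3 = 21 are under the blank column. That assumes no delays or surgical pauses, which section 6.4 allows, and treatment through week 48. It also includes maintenance, where Table 4's FOLFIRINOX rules no longer apply and the lead sentence of section 5.3, which names the combination, leaves it unclear whether the list applies.

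**Conclusion.** The concern holds as an internal inconsistency in an operative schedule. Table 5.1 and section 5.3 disagree on three laboratory panels for cycles 4 to 12: 9 of 12 chemotherapy cycles and 9 of 11 retreatment decisions. Maintenance is less settled, because the table is blank there too and section 5.3 may not reach it.

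The conclusion rests on the cell alignment in step 2 and on the 12 planned cycles. How many sites would follow the table over the text cannot be known from the protocol, so the effect on observed toxicity rates is a risk without a number. The phase II primary endpoint and its decision rule are not affected. The correction should be made because it concerns patient safety and costs almost nothing.

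**What to change.** Confirm the three blanks against the source PDF. Then reconcile table 5.1 with section 5.3 and with Tables 4, 9 and 10, so that table and text give one laboratory schedule from cycle 4 on. State explicitly which schedule applies during regorafenib maintenance. Which schedule is clinically right is for the sponsor and investigators to decide.

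As a minor point, reword the timing phrase in section 5.3 so that the ± 3 days is clearly consistent with assessment before treatment.

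The cost is a few marks in a table and a phrase in an amendment. If section 5.3 reflects the intent, no test is added.

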**The following assessments should be performed on day 8 of cycle 1, 2 , 3 :**

- A CBC with differential should be performed: RBC, hemoglobin, hematocrit, platelet count and WBC. WBC must include differential neutrophil, lymphocyte, monocyte, basophil and eosinophil counts
- Chemistry panel: albumin, total protein, lipase, glucose, serum creatinine, clearance calculated according MDRD, uric acid
- Liver function test panel: Aspartate Amino-Transferase (AST), Alanine Amino-Transferase (ALT), bilirubin (total and direct), GGT, Lactic Dehydrogenase (LDH)

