**Prophylactic G-CSF will be systematically given after each course from Day-7 to Day 12.**

**REGORAFENIB** will be given orally at a dose of 80 to 160 mg, as per dose-level, once daily on days 4 to 10 of each cycle

Tumor assessments (computed tomography (CT) or magnetic resonance imaging (MRI)) of the chest, abdomen, pelvis (if patient allergic to iodine contrast agents) will be performed at the baseline, every 8 weeks thereafter.

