from Schultheis et al. (10) was designed to explore whether addition of regorafenib to FOLFOX or FOLFIRI could be feasible as a treatment of mCRC, in terms of safety and pharmacokinetic interactions of the various drug components of the regimen. Forty-five patients were treated every 2 weeks with 5-fluorouracil 400 mg/m^2 bolus then 2400 mg/m^2 over 46 h, folinic acid 400 mg/m^2, and either oxaliplatin 85 mg/m^2 or irinotecan 180 mg/m^2. On days 4–10, patients received regorafenib 160 mg orally once daily. Drug-related adverse events resulted in dose modification, dose interruption, or permanent discontinuation of study treatment in 31 (69%) patients overall (18 [72%] FOLFOX and 13 [65%] FOLFIRI). Dose reduction or dose interruption of at least one of the chemotherapy components was observed in 52% of patients treated with FOLFOX and 65% of patients receiving FOLFIRI. A dose reduction of 5-fluorouracil due to AEs was necessary in 18% of administered cycles. 5-Fluorouracil administration was omitted in 8% of cycles. Oxaliplatin and irinotecan doses were reduced in 11% and 12% and interrupted in 11% and 5% of administered cycles, respectively. Actually, regorafenib had acceptable tolerability in combination with chemotherapy. The most frequent grade 3-4 AEs were: neutropenia (45%), Hand-Foot Skin Reaction (15%), diarrhea (10%), and hypophosphatemia (12%). Regarding pharmacokinetics, area under the curve (AUC) of irinotecan was significantly higher in cycle 2 (following regorafenib dosing) than in cycle 1 (before regorafenib dosing); the ratio of AUC values (cycle 2:cycle 1) was 1.28 (90% confidence interval [CI] 1.06 –1.54). Cmax of irinotecan was only slightly increased, and t1/2 was unchanged. For SN-38, AUC was significantly higher in cycle 2 than in cycle 1 (ratio 1.44, 90% CI 1.12–1.85), while Cmax was unchanged. In line with the known elimination pathways of platinum and 5-fluorouracil, no pharmacokinetic interaction with regorafenib was seen (10). The study from O'Neil et al. (11) was designed to show whether the addition of regorafenib to FOLFIRI improves PFS (over a placebo-FOLFIRI arm) when given as second-line therapy for patients treated initially with oxaliplatin and fluoropyrimidine-based therapy. The regorafenib/FOLFIRI schedule that was used was the one proposed by Schultheis et al. (10) (i.e. standard FOLFIRI with irinotecan 180 mg/m^2 plus regorafenib 160 mg daily from day 4 to 10). The study met its primary endpoint of demonstrating that the addition of regorafenib to FOLFIRI prolongs PFS compared to FOLFIRI alone with a HR of 0.72. When looking at tumor response, authors found that regorafenib (combined to chemo) provided more partial responses than placebo plus chemo (35% vs. 19%, p= 0.045). The combination was very tolerable, with little increase in toxicity compared to the control chemotherapy regimen. Of note, regarding the top-3 reported severe (gr. 3-4) AEs, neutropenia, diarrhea, and hypophosphatemia were reported in 41%, 15%,

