**With this treatment, prophylactic G-CSF will be systematically given after each course from Day 7 to Day 12.**

### **REGORAFENIB administration (Phase I and II):**

-On days 4–10 of each cycle, all patients will receive Regorafenib orally once daily depending on dose levels for phase I and RPD2 for phase 2.

- 1 cycle = 15 days

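### Phosphate is not scheduled on any regorafenib dosing day, so transient grade 3 or higher hypophosphatemia may be under-detected in the DLT window

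*Combined protocol and SAP*

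**What the plan says.** **Dosing.** The synopsis (treatment modalities) gives regorafenib "once daily on days 4 to 10 of each cycle", and section 6.1 repeats those days for both phases. On cycle length, section 6.1 says under FOLFIRINOX "The next cycle starts on day 15. Each cycle will be delivered every 2 weeks" and under regorafenib "1 cycle = 15 days".

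**Day 1 of each cycle.** Section 5.3 lists "Electrolyte panel: sodium, potassium, chloride, magnesium, calcium, bicarbonates, phosphate". Day 1 assessments are to be done "prior to receiving study treatment (+/- 3 days").

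**Day 8 of cycles 1, 2 and 3.** Section 5.3 lists a blood count, liver tests and "Chemistry panel: albumin, total protein, lipase, glucose, serum creatinine, clearance calculated according MDRD, uric acid". The visit table in section 5.1 leaves the electrolyte row blank at C1D8, C2D8 and C3D8. Its footnote 6, which defines the chemistry panel, does not include phosphate.

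**Outside the cycles.** Phosphate is also drawn at screening (section 5.2, under electrolytes) and at end of treatment (section 5.4, under chemistry). Neither falls on a dosing day.

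**Known risk.** Of the randomised second-line trial of FOLFIRI with regorafenib or placebo, the background (section 1, Regorafenib) says: "regarding the top-3 reported severe (gr. 3-4) AEs, neutropenia, diarrhea, and hypophosphatemia were reported in 41%, 15"%. The sentence goes on to 14% for hypophosphatemia, against 0% on placebo. The earlier study of regorafenib with FOLFOX or FOLFIRI is reported at 12%.

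**DLT rule.** Section 2.2.1 counts drug-related non-hematologic toxicity of grade 3 or higher in the first three cycles. The exceptions cover nausea, vomiting, diarrhea, alopecia, controllable HFSR and lipase elevation without pancreatitis. Hypophosphatemia is not among them.

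**The concern.** The phase I primary endpoint is adverse events plus DLT incidence at each dose level in cycles 1 to 3, and with 3 to 6 patients per level one event can change the escalation decision. The protocol itself names low phosphate as a leading severe toxicity of regorafenib with a chemotherapy doublet. It nevertheless schedules the test only before dosing starts or some days after it ends. A dip that appears during the seven tablet days and recovers before the next day 1 has no planned measurement that would find it.

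The contrast with other tests is hard to explain. Liver tests are done weekly in these cycles. Lipase is on the day 8 list although its isolated elevation is exempt from the DLT definition. Phosphate, which is not exempt, is not on that list.

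**Working it through.** The plan states no figure to reproduce here, so the check is a calendar count.

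**Inputs**
- Tablet days 4 to 10 (synopsis; section 6.1).
- Cycle length L = 14 days (next cycle on day 15), or 15 days under the other statement in section 6.1.
- Phosphate on day 1 only, window of 3 days either way (section 5.3).
- Day 8 draw in cycles 1 to 3, without phosphate (sections 5.1 and 5.3).
- DLT assessment from C2D1 to C4D1 (section 5.3).

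**Step 1: calendar.** In cycle c, tablets fall on study days L(c-1)+4 to L(c-1)+10, the day 1 draw on L(c-1)+1 and the day 8 draw on L(c-1)+8. With L = 14:
- tablets: days 4-10, 18-24 and 32-38, or 3 x 7 = 21 dosing days;
- phosphate: days 1, 15, 29 and 43;
- day 8 draws: days 8, 22 and 36.

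None of the phosphate days is a tablet day. Day 1 of cycle 1 is before any exposure, so the DLT window holds three post-exposure values: C2D1, C3D1 and C4D1.

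**Step 2: gap from last tablet to next phosphate value.** Gap = (L + 1) - 10.
- L = 14: 15 - 10 = 5 days; with the window, 5 - 3 = 2 to 5 + 3 = 8 days.
- L = 15: 16 - 10 = 6 days; with the window, 3 to 9 days.
- Cycle delayed to day 29, the limit in Table 4: 29 - 10 = 19 days.

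The number of scheduled phosphate values on a tablet day in cycles 1 to 3 is 0 in every variant.

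**Step 3: what day 8 would add.** Day 8 is tablet day 8 - 4 + 1 = 5 of 7. Adding phosphate there raises scheduled on-drug values per patient in the DLT window from 0 to 3.

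**Step 4: how much one event can matter.** Assume that the cited 12% and 14% apply per patient within cycles 1 to 3 of this regimen. The documents do not say so.
- At least one case among 3 patients: 1 - 0.88^3 = 32%; 1 - 0.86^3 = 36%.
- A level meets the 3+3 stopping rule from this toxicity alone, as P(2 or more of the first 3) + P(exactly 1 of the first 3) x P(1 or more of the next 3): 0.040 + 0.279 x 0.319 = 13%; 0.053 + 0.311 x 0.364 = 17%.

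These are frequencies of the event under that assumption. They are not frequencies of a missed event.

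**The case against.** The schedule facts are not in dispute. The consequences are, and most of the case against them stands.

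- **Bias.** A reader might infer that the DLT rate is biased downwards at every dose level. That requires phosphate to have largely recovered by day 15, and the documents give no nadir, recovery time or regorafenib half-life. One could assume a recovery half-time of 2, 3 or 5 days and find 0.5^(5/2) = 18%, 0.5^(5/3) = 31% or 0.5^(5/5) = 50% of a deficit left after 5 days. Nothing in the documents supports those half-times, and a remaining fraction of a deficit is not a fraction of missed grade 3 events. Section 6.9 also describes likely enterohepatic circulation of regorafenib and its metabolites, so a day without a tablet is not a day without drug.
- **Cited rates.** Both studies used the same day 4 to 10 schedule, and the documents do not say when phosphate was drawn. The 12% and 14% may have been found with similar sampling. They come from doublets plus regorafenib, so a reader should not take them as rates for FOLFIRINOX plus regorafenib.
- **What counts.** Section 11.1.1 makes a laboratory finding an adverse event only when it is clinically significant, for instance when it calls for intervention. A dip that resolves untreated may not be an event or a DLT. The reply is only partial: clinical significance cannot be judged for a value never taken.
- **Other routes.** Three day 1 values remain, timed with the DLT assessments. Adverse events are collected continuously and unscheduled tests are possible. Persistent, cumulative or symptomatic cases can be caught, so low phosphate is not simply left undetected.
- **Other electrolytes.** The documents cite no regorafenib signal for potassium, magnesium or calcium, so the case for day 8 testing covers phosphate only.

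None of this supplies a planned phosphate value during dosing.

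**Conclusion.** The gap is certain: within cycles, phosphate is scheduled only on day 1, about 5 days after the last tablet (2 to 8 with the window), and no draw in the DLT window falls on a dosing day. This holds for either stated cycle length.

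The supported consequence is limited. Transient grade 3 or higher hypophosphatemia on drug may be under-detected in cycles 1 to 3, for a toxicity that the background ranks among the top three severe events with regorafenib plus FOLFIRI and that the DLT definition does not exempt. The size cannot be computed from the documents. A definite downward bias in the DLT rate, or a stated share of missed events, would go beyond them. The point is worth acting on because the remedy is cheap and bears on a phase I primary endpoint and on patient safety.

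**What to change.** - Add phosphate to the existing day 8 blood draw of cycles 1, 2 and 3, in section 5.3 and in the section 5.1 visit table.
- For each of these cycles, report the worst of the day 8 value and the following day 1 value (C2D1, C3D1 or C4D1) as a laboratory summary by dose level. Adverse event and DLT classification should still follow sections 11.1.1 and 2.2.1, so the summary does not create a new DLT criterion.
- List phosphate under the same panel throughout. It is under electrolytes at screening and on day 1 but under chemistry at end of treatment, so a site could misread the day 8 chemistry panel as including it.
- Reconcile the two statements of cycle length in section 6.1, since the sampling days depend on them.

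Cost: one analyte at three visits, on blood already drawn, with no extra visit or puncture. Recorded laboratory abnormalities may rise slightly.
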